#### 11.2. Assessment of Compliance

Compliance will be documented by recording the date and time of the administration in the CRF. The number of IV infusions actually administered to each patient will be calculated as the percentage of the total number of IV infusions planned per protocol and will provide a measure of treatment compliance. All treatment cycles and efficacy

evaluations will be performed within a window of  $\pm 3$  working days.

#### 11.3. Risk assessment and Precautionary Measures

The investigational medicinal product is clinical use for many years and has demonstrated a very benign safety profile. The safety information for the IMP is provided in the SmPC in Appendix 1.

# 12. STUDY AND TREATMENT DURATION

Study/Treatment start:05 / 2020Study/Treatment end:12 / 2025

#### 13. STATISTICAL METHODS

The final statistical analysis of the study will be performed by a qualified biometrician and will fulfill all ICH/GCP requirements for handling of clinical study data. The statistical analysis, including any subgroup analysis will be agreed upon prior to data evaluation and the results will be fixed in a statistical analysis plan (SAP). The study data will be analysed and the Statistical Report written as soon as all study data are entered into the study data base and the entered data are validated.

#### 13.1. **Preliminary Remark**

Although this study is intended to be of exploratory nature, the analysis will be based on 'confirmatory' principles with pre-specification of the primary analyses and control of multiple level alpha.

#### 13.2. Primary Objective

It is the primary objective of this study to assess the efficacy of Cerebrolysin versus Placebo upon a battery of co-primary neurocognitive outcome scores at 6 and 12 months after baseline.

#### **13.3. Primary Efficacy Criteria**

#### 13.3.1. Justification for Multi-Dimensional Approach

To address the multidimensional breadth of cognitive impairment/recovery in patients after stroke, the primary endpoint of trial is defined as a multidimensional cognitive endpoint, combining the various cognitive dimensions by a global, multidimensional, correlation-sensitive approach. This way the primary cognitive objective can be defined in terms of a combination of individual effects across the single cognitive endpoints, thus substantially enhancing the assay sensitivity and strength of evidence. The procedure is the generalized Wilcoxon-Mann-Whitney test (Wei-Lachin procedure).

#### 13.3.2. Defined Efficacy Ensemble

The following ensemble of appropriate single efficacy criteria shall be tested by a multivariate, directional test approach, reflecting the cognitive status of patients with Acute Ischemic Stroke at 180 and 360 days after baseline:

#### Multivariate Efficacy Ensemble

- Stroop test (Stroop)
- Trail-Making-Test Part A (TMT-A)

- Digit Span Backwards Task (DS-BW)
- Digit Symbol (DS-WPSI)
- Verbal Fluency Test CFL Version (VFT-CFL)
- Rey Auditory Verbal Learning Test (RAVLT)

#### 13.4. Secondary Objectives

It is the secondary objective of this clinical study to assess the efficacy of Cerebrolysin versus Placebo upon a battery of the co-primary neurocognitive outcome scores at 180 and 360 days after baseline as well as to assess the efficacy of Cerebrolysin versus Placebo on neurological deficit, functional outcome, symptoms of anxiety and depression and drug safety at 180 and 360 days after baseline.

#### 13.5. Secondary Variables

- Score and score changes from baseline of the individual primary outcome scales at 180 and 360 days after baseline
- Score change from baseline of the NIH Stroke Scale at 180 and 360 days after baseline
- Modified Rankin Score at 180 and 360 days after baseline
- Score change from baseline of the Hospital Anxiety and Depression Scale at 180 and 360 days after baseline
- EQ-5D-5L at 180 and 360 days after baseline.
- Drug Safety parameters including Adverse Events

#### 13.6. Level of Significance

The multiple level alpha is set to  $\alpha$  = 0.05, two-sided.

#### 13.7. Multiplicity

Multiplicity regarding multiple primary outcome measures is controlled by the chosen correlation-sensitive, multivariate test procedure (Wei-Lachin procedure, see also section 13.9).

Mutiplicity regarding the two primary points in time is controlled by means of the principle of *a priori* ordered hypotheses (fixed sequence approach). The procedure of *a priori* ordered hypothesis is most powerful with full control of alpha (for control of alpha using stepwise testing see Maurer W, Hothorn LA, Lehmacher W 1995). The sequence and nature of the a priori ordered test-statistical hypotheses of the trial is defined as follows:

- 1. Combined cognitive outcome measures as defined in section 13.3.2, score changes from baseline to day 180 (month 4 post stroke), multivariate analysis, generalized Wilcoxon-Mann-Whitney test (Wei-Lachin procedure)
- 2. Combined cognitive outcome measures as defined in section 13.3.2, score changes from baseline to day 360 (month 13 post stroke), multivariate analysis, generalized Wilcoxon-Mann-Whitney test (Wei-Lachin procedure)

The principle of *a priori* ordered hypotheses is embedded in the well-known general principle of closed testing. The pre-planned chain of hypotheses can be tested in a confirmatory way with the same full alpha value; each test result smaller than alpha will be statistically significant as long as the preceding test result was also significant.

#### 13.8. Sample Size Calculation

The power for this study is determined based on the following design specifications:

- Two-sided type I error defined as alpha = 0.05, two-sided (multiple level alpha, see section 13.6)
- Type II error defined as  $\beta = 0.1$  (Testpower 90%)
- Design alternative effect size: Mann-Whitney statistic (MW) = 0.60 (small to medium-sized difference according to Cohen (Colditz, 1988); assuming a normal distribution the effect size MW may easily be re-expressed as the well-known Cohen effect size (Cohen, 1988) of a standardized difference (Cohen's d): MW = 0.60 means Cohen's d = 0.35)
- Estimated correlations among the single outcome scales included in the global statistics  $\rho = 0.6$ )

Nonparametric sample size calculations within the framework of a multiple outcome approach (Wei-Lachin procedure- Wei and Lachin, 1984; Lachin 1992) was performed applying the validated software Nnpar 1.0 from idv Data Analysis and Study Planning, Krailling/Munich (see also Tang, 1999; Lachin, 1981). A good example for sample size calculation according to the Lachin approach (Wei and Lachin, 1984; Lachin 1992; Lachin, 1981) in multidimensional trials with neuroprotective agents is also given by Huang (2008).

Please note: further details of the effect size (Mann-Whitney statistic) are described in section 13.9, further details of sample size assessment are described in the separate document "Sample Size Assessment Based on a Multidimensional Efficacy Approach".

Based on the above design specifications, the total required sample size for the multivariate ensemble results in 145 patients per group (including 15% enhancement for usual "ambiguities", e.g., dropouts). With this sample size a "small to medium-sized" group difference (MW = 0.60) with regard to the multivariate cognitive outcome ensemble can be detected with a power of 90%.

#### 13.9. Confirmatory Analyses

Minimizing the required assumptions is a recommended approach for confirmatory statements on efficacy (LaVange, 2005). This applies especially in scales with skewed distributions including floor and ceiling effects as is known from many cognitive scales. Furthermore, data types can be of different nature (binary, ordinal, continuous). Thus, a nonparametric assessment of treatment effects independent of data type and distribution is the method of choice for the primary analysis.

The nonparametric analysis will be performed using the Wei-Lachin procedure, a multivariate generalization of the Wilcoxon-Mann-Whitney test, which takes account of the correlation among univariate Mann-Whitney tests for each outcome to produce an overall average estimate of benefit and test for treatment differences. The summarizing test used is, however, not the undirectional or omnibus test of the classical procedure, but instead the directional test which is most efficient in the case of known direction for superiority (as is the case for the selected outcome scales).

The procedure is described by Wei and Lachin (1984), Lachin (1992), and Lachin (2014). Practical examples are given in modern textbooks on multiple testing problems (see e.g., Dimitrenko, 2009). Incidentally it should be noted that the nonparametric Wei-Lachin procedure is similar to the frequently used parametric procedure of O'Brien (O'Brien, 1984). We prefer, however, the Wei-Lachin procedure as it is more robust for practical data sets (minimization of required assumptions (LaVange 2005)) and because the O'Brien procedure has been shown to give too liberal results (Frick 1997).

It is important to note, that the multivariate, directional test procedure chosen for this study can cope simultaneously with binary, ordinal and continuous data. Thus, there is no technical need for the widely used dichotomization of original scales which is associated with substantial loss of information and reflects a major disadvantage of previous Stroke studies.

The effect size measure directly associated to the Wilcoxon-Mann-Whitney test is the Mann-Whitney statistic. It is recommended by many authors for its sensitivity and robustness in all data situations (Agresti et al. 1984, Brunner et al. 2000, Munzel et al. 2003, D'Agostino et al. 2006, Brunner et al. 2013, Kieser et al. 2013). For

ordinal/rating scales it is regarded as method of choice or 'gold standard', see also Design and Analysis of Non-Inferiority Trials (Rothmanns et al. 2011).

Technically, the MW gives the probability that a randomly chosen patient of the test group is better off than a randomly chosen patient of the comparison group (with the probability ranging from 0 to 1, with 0.5 indicating equality); it is statistically defined as: P(X < Y) + 0.5 P(X = Y).

Applying the Mann-Whitney effects size measure, the null and alternative hypothesis for the comparisons of the test treatment to control treatment (superiority) can be formulated as follows:

The traditional benchmarks for the Mann-Whitney effects size measure (MW) are as follows (Colditz,1988):

- 0.29 large inferiority
- 0.36 medium inferiority
- 0.44 small inferiority
- 0.50 equality
- 0.56 small superiority
- 0.64 medium superiority
- 0.71 large superiority

The confirmatory analyses are performed with the FAS population according to the ICH Guideline E9 (full analysis set). Since the use of the per protocol set, however, maximises the opportunity for a new treatment concept to show additional efficacy in the analysis, and most closely reflects the scientific model underlying the protocol (see ICH E9, section 5.2.2), the supportive analysis by means of the per-protocol set will be regarded as of equal scientific importance (see also Schwartz 1967, Schwartz 1980, Senn 2007).

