#### 4. STUDY OBJECTIVES

This study shall assess the efficacy of pharmacological intervention with Cerebrolysin in the prevention of post stroke cognitive decline.

The aim of this trial is to test the hypothesis that patients randomized to Cerebrolysin show improved cognitive outcome measured with a battery of co-primary neuropsychological tests as compared to patients randomized to placebo (multivariate analysis of combined cognitive outcome measures).

Furthermore, it is intended to investigate the hypothesis that Cerebrolysin, as compared to placebo, will show improved scores at four, seven and thirdteen months post-stroke on neurological deficit, global function, depression and anxiety. In addition, it is intended to investigate the effects of Cerebrolysin versus Placebo on the Quality of Live at seven and thirdteen months after stroke. Furthermore, it is intended to evaluate the safety of Cerebrolysin in patients with recent stroke and to determine which demographic, clinical and radiological characteristics predict response to treatment with Cerebrolysin.

Other study designs, including non-randomised controlled trials, can detect associations between an intervention and an outcome. But they cannot rule out the possibility that the association was caused by a third factor linked to both intervention and outcome. Random allocation ensures no systematic differences between intervention groups in factors, known and unknown, that may affect outcome. Double blinding ensures that the preconceived views of subjects and clinicians cannot systematically bias the assessment of outcomes. Intention to treat analysis maintains the advantages of random allocation, which may be lost if subjects are excluded from analysis through, for example, withdrawal or failure to comply. Meta-analysis of controlled trials shows that failure to conceal random allocation and the absence of double blinding yield exaggerated estimates of treatment effects.

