#### 13.12.4. Per Protocol Population (PP)

A sensitivity analysis will be performed for a per protocol (PP) data set as an exploratory approach. The PP population includes all patients who are eligible for FAS evaluation and who additionally do not show major protocol deviations. As noted in section 13.9, the supportive analysis by means of the per-protocol set will be regarded as of equal scientific importance as the FAS analysis, since it most closely reflects the scientific model underlying the protocol (see ICH E9, section 5.2.2).

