#### 13.14. Compliance

Patients with compliance for the entire study below 80% for the treatments will be considered protocol violators and will not be included in the per protocol analysis.

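### The per-protocol analysis is ranked equal to the confirmatory full analysis set with no rule for disagreement, and its whole-study compliance cut-off lets events after day 180 decide who is in the day-180 comparison

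*Protocol*

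**What the plan says.** Protocol 13.9 names the FAS as the population for the confirmatory analyses. It then says that "the supportive analysis by means of the per-protocol set will be regarded as of equal scientific importance". One reason given is that the PP set gives the new treatment the best chance to show additional efficacy; the other is that it is closest to the scientific model behind the protocol.

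Section 13.12.4 introduces the same analysis differently: "A sensitivity analysis will be performed for a per protocol (PP) data set as an exploratory approach". It then repeats the equal ranking with the FAS.

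Section 13.12.3 assigns all efficacy analyses to the FAS. Section 13.7 controls multiplicity across the six scales (Wei-Lachin procedure) and across the two time points (fixed sequence, day 180 then day 360). Analysis sets are not mentioned there.

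On who enters the PP set, 13.14 says: "Patients with compliance for the entire study below 80% for the treatments will be considered protocol violators", and removes such patients from the PP analysis. Section 11.2 defines compliance as infusions given divided by all infusions planned per protocol. Section 13.12.4 defines one PP set, not one per visit.

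Section 4 defends intention-to-treat analysis because it keeps the advantages of random allocation, "which may be lost if subjects are excluded from analysis through, for example, withdrawal or failure to comply".

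**The concern.** An analysis cannot be exploratory and also rank equal to the confirmatory one. The hypotheses in 13.9 are superiority hypotheses. Preferring a set because it favours showing an effect is a reason for caution there, not for promotion, and it sits badly with Section 4's own argument against excluding non-compliers. If the FAS result is negative and the PP result positive, the protocol supplies words for presenting the PP result as an answer of the same weight and no rule against doing so.

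The second problem is one of timing. Day 180 is the first ordered hypothesis. Under the four-cycle schedule the last ten infusions fall on days 241-250, after Visit 3. A cut-off on whole-study compliance therefore lets behaviour or events after the day-180 assessment decide whether that assessment counts in the PP set. Read literally, a patient who dies before receiving 80% of the planned infusions also leaves the PP set, although 13.11.1 argues for keeping deaths in the analysis so that the arm with more deaths does not look better.

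**Working it through.** **Inputs**

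- Error rate (13.8): "Two-sided type I error defined as alpha = 0.05, two-sided", so 2.5% in the favourable direction.
- Compliance cut-off (13.14): 80% over the entire study, denominator as in 11.2.
- Schedule (synopsis, 7.1.1, 11.1): four cycles of 10 infusions on days 1-10, 61-70, 121-130 and 241-250, which makes 40 in total, 30 of them before day 180.
- Schedule as described in Section 5: three courses only, 30 infusions.
- PP retention: not given. Assumed 90% to 70% of the FAS.

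**The plan's own figure.** The sample size is not at issue, but it can be approximated. The inputs in 13.8 are "Mann-Whitney statistic (MW) = 0.60", expressed there as d = 0.35, a correlation of 0.6 and 90% power; 13.3.2 lists six scales. The variance factor is (1 + 5 × 0.6)/6 = 0.667. Then n = 2 × (1.960 + 1.282)² / 0.35² × 0.667 = 114.4 per group. Dividing by 0.955 (efficiency of the Wilcoxon test relative to the t-test) gives 119.8, rounded up to 120, and 120/0.85 rounds up to 142, against the stated 145. Other six-scale variants give 127 to 138, so 145 is not too small.

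**Step 1: error rate if either set may carry the claim.** If patients are removed without regard to outcome, the FAS and PP test statistics under the null are approximately bivariate normal with correlation √(n_PP/n_FAS). P(either) is the probability that at least one exceeds 1.96 in absolute value. P(both) = 0.05 + 0.05 − P(either).

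| PP as share of FAS | Correlation | Either, two-sided | Either, favourable direction | Both, two-sided |
|---|---|---|---|---|
| 90% | 0.949 | 6.5% | 3.2% | 3.5% |
| 85% | 0.922 | 6.8% | 3.4% | 3.2% |
| 80% | 0.894 | 7.1% | 3.5% | 2.9% |
| 70% | 0.837 | 7.6% | 3.8% | 2.4% |

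FAS alone: 5.0% two-sided, 2.5% in the favourable direction.

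**Step 2: what selection could add (illustration only).** This is a null simulation of the directional six-scale rank test with 123 per arm (145 × 0.85) and 6,000 runs per setting. In the active arm, exclusion had correlation 0.3 with poor outcome; in the placebo arm it was random. The favourable-direction error of the PP test alone was 5.8% with 10% excluded and 8.3% with 15% excluded, against 2.5%. With 15% excluded and the same selection in both arms it was 2.8%. The bias therefore depends on exclusion being related to outcome differently by arm, which the protocol cannot show.

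**Step 3: compliance.** On 40 planned infusions, 80% means at least 0.80 × 40 = 32.

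- All 30 before day 180, none in cycle 4: 30/40 = 75.0%, excluded.
- All 30, one in cycle 4: 31/40 = 77.5%, excluded.
- All 30, two in cycle 4: 32/40 = 80.0%, kept.
- The same patients counted only to day 180: 30/30 = 100%, kept.

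On Section 5's three courses the denominator would be 30 and the first patient would have 100%. The result therefore turns on which description of the schedule applies.

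**The case against.** The strongest reply is that the formal error rate is not touched. Sections 13.9 and 13.12.3 put the confirmatory tests on the FAS, 13.7 lists two ordered hypotheses with no PP step, and no passage lets a significant PP result replace a failed FAS test. That stands. A reader might infer that the trial's 5% level is not controlled; the documents do not support this. The equal ranking also states no decision rule: it could be read as asking both sets to agree, which would be conservative (2.4% to 3.5% in Step 1). And 13.9 gives a second reason for the PP set, its closeness to the scientific model, which is a legitimate reason to report it.

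There are safeguards too. Sections 13.12.1 and 13.15 allocate patients to sets in a blind review before decoding, so the PP set cannot be chosen with knowledge of allocation. That does not remove selection on events after randomisation.

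On compliance, a reader might infer that fully dosed patients in general are removed. In fact it concerns only patients fully dosed to day 180 who then receive none or one of the cycle-4 infusions, and 7.1.1 allows missed infusions to be added at the end of a course. The protocol gives no figure for how many this would be, and the FAS test at day 180 is unaffected.

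What remains is wording, stated twice, that contradicts the exploratory label and leaves disagreement between the sets unresolved, together with a compliance rule that does not fit the first time point.

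**Conclusion.** The point holds as an inconsistency and a missing rule, not as a loss of formal error control. The FAS tests keep their 5%. Only if a positive claim were accepted from either set would the two-sided error rise to about 6.5% to 7.6% (3.2% to 3.8% in the favourable direction), and then at assumed PP retention of 90% to 70% with removal unrelated to outcome. Selection related to outcome in one arm could add more, but its size and direction cannot be derived from the protocol.

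The day-180 exclusion (75.0% or 77.5% against 80%) follows from 11.2, 13.12.4 and 13.14 under the four-cycle schedule. It does not arise under Section 5's three courses. It affects only the PP result, which matters more because that result is ranked equal to the FAS. This should be fixed before unblinding; it does not invalidate the confirmatory analysis.

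**What to change.** 1. In 13.9 and 13.12.4, delete the wording that ranks the PP analysis equal to the FAS. State that the FAS alone decides both ordered hypotheses and that the PP analysis is supportive only, whatever its result.
2. In 13.14, with 11.2, compute PP compliance separately for each time point, from the infusions planned up to the visit analysed.
3. Reconcile Section 5 (three courses) with the synopsis, 7.1.1 and 11.1 (four cycles), so that the compliance denominator is defined.

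The statistical changes are wording only and need no extra patients or data. The sponsor gives up the PP result as a fallback claim, and two PP sets must be listed instead of one.

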#### 13.10. Exploratory Analyses

All primary and secondary efficacy criteria will be analyzed with descriptive group statistics.

In addition, nonparametric effect sizes and confidence intervals (Mann-Whitney effects size measure) will be provided for all primary and secondary efficacy criteria at all points in time.

#### 13.11. Accounting for missing data

#### 13.11.1. Missing Data Problems – General Considerations

Missing data are a problem in every data analysis. Of course, there are always missing data of the type 'missing completely at random' (MCAR), which in principle will not bias the results; the analysis procedure should be able to cope with partially missing data of such a type. In many studies this type of data is treated by LOCF replacement (Last Observation Carried Forward) as far as there exist follow-up measurements at previous visits.

In a study like the one planned there might also be informatively missing data (missing not at random, MNAR): participants of the study died or are unable to complete the tests because of brain-related impairment. Neglecting these missing data might introduce bias.

A reasonable policy for minimizing bias in the case of informatively missing data (MNAR) is the replacement of these missing data by assigning the worst possible score, or a score worse than those observed. It should be noted that this strategy is only reasonable if rank-based robust procedures are used for the data analysis.

The worst rank imputation procedure was recommended by Lachin in his seminal paper about the missing data problem for data missing because of mortality when performing an exercise test (Lachin, 1999). This procedure was also used when analyzing non-fatal outcomes in studies where mortality was a problem (Lusben, 2002; McMahon, 2001). Recently a similar procedure has been proposed by the 'Traumatic Brain Injury (TBI) Clinical Trials Network' when designing the COBRIT study (Bagiella, 2010).

Temkin (2007) included deaths with the worst rank for the significance tests of neuropsychological scales but excluded deaths for the calculation of descriptive statistics (e.g., mean, SE estimates). Thus, significance tests reflect all patients with estimation of missing data while the descriptive statistics reflect only the actually observed assessments. We prefer not excluding deaths from descriptive statistics, since the study treatment with more deaths would artificially have better neuropsychological scores while a study treatment preventing deaths would be burdened by rather severe scores of survived patients. The use of robust descriptive statistics in this study allows the inclusion of worst rank scores for deaths also in

descriptive analysis. This way, confirmatory analyses and descriptive analysis can be based on the same analysis data and contradictory results are avoided.

